
^j At Screening, send patient for structured clinical interview if one or more positive mMIDI modules. If the structured clinical interview confirms that the subject does not have an ICD, he/she will not be considered ineligible on that basis. After Baseline, if patient has one or more positive modules on the mMIDI, their continued participation in the study should be discussed with the Medical Monitor.
 
^k The 3-day practice diary during the Screening Period and the 3-day Baseline diary must both be valid in order to enroll a patient. The trainer/rater will call the patient before the scheduled start of the diary completion periods to remind him or her to keep the PD diary and to review completion instructions. The patient will also be reminded to send the completed practice diary to the trainer/rater and to bring their Baseline diary to the Baseline Visit. If the practice or Baseline diary is invalid, the patient may be retrained and complete another practice or Baseline diary within the 6-week window of the Screening Period, if the patient is otherwise eligible for the study.
 
^l PD diary collected over the 3 consecutive 24-hour periods before the day of the scheduled study visits on Weeks 12, 24 and 52. The PD diary trainer/rater will call the patient before the scheduled start of the 3-day PD diary completion period (at the latest, on the last working day before the scheduled start of the PD diary completion) and review completion instructions. The patient will also be reminded to bring their PD diary to the visit. The trainer/rater will instruct the patient if the PD diary contains missing and/or invalid entries to reinforce instructions for appropriate completion.
 
^m Done only if the ET date coincides with the scheduled diary collection return date.
 
ⁿ Pretreatment AEs.
 
^o Hematology tests: Hemoglobin concentration, hematocrit, red blood cell count, total and differential white blood cell, thrombocyte (platelet) count.
 
^p Blood chemistry (including liver function) tests: Aspartate amino transferase (AST), alanine amino transferase, (ALT), gamma-glutamyl transpeptidase (GGT), alkaline phosphatase (ALP), lactate dehydrogenase (LDH), total bilirubin (conjugated and unconjugated), albumin, creatinine, urea/BUN, bicarbonate, uric acid, total protein, sodium, chloride, potassium, calcium, phosphate, glucose, cholesterol, creatine phosphokinase (CK).
 
^q TSH, free T₃, and free T₄.
 
^r For applicable patients: At Screening, document method of contraception used by patient. At subsequent visits, verify continuation of (or any change to) contraceptive method.
 
^s For females of childbearing potential: urine pregnancy test.
 
^t Urinalysis: Specific gravity, pH, ketones, blood, protein, glucose. If urine dipstick is positive for leukocytes, protein, or erythrocytes, a microscopic evaluation and culture will be performed.
 
^u A PK blood sample should be collected at the most convenient time during the Week 2 visit. Record the patient-reported date and approximate time when the patient took the most recent dose of IMP. Record the date and time of the PK sample collection. See Section 8.0 of the protocol. (Note: sites participating in Expanded PK Sampling should refer to Appendix 15.9.)
 
^v Patients will be instructed to take the assigned dose of open-label tozadenant by mouth BID, in the morning and in the evening preferably at the same time each day. The evening dose should be approximately 12 hours after the morning dose. Patients will be instructed to take their morning and evening doses at least 1 hour before or 2 hours after a meal and to refrain from eating for at least 1 hour after dosing.
 
^w If patient has discontinued IMP, perform Early Termination Visit as soon as possible after the last dose of IMP. If patient took the last dose of IMP 28 or more days prior to the Early Termination Visit, a Safety Follow-Up Visit (Section 6.2.19) is not required.

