5.8 Procedures for Monitoring Patient Compliance

After IMP is dispensed, at each subsequent study visit patients must return all used, unused, and partially used clinical IMP supplies. Drug accountability must be done in the patient's presence in order to obtain explanations regarding discrepancies in compliance with the dosing regimen. Drug accountability must be recorded on the Drug Accountability Form. Upon completion of the patient's Visit 8 at Week 52 (or Early Termination Visit, whichever occurs first), the authorized study staff will enter the date of the last dose of IMP taken in the source documents and eCRF to register the end of treatment for that patient.

If a patient is found to be persistently noncompliant (≤ 80 to $\geq 120\%$ of the assigned dose), the Sponsor/Sponsor's designee, in conjunction with the investigator, will make a decision as to whether the patient should be discontinued from the study.

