9.3. Treatments

9.3.1. Extent of Study Drug Exposure

The number of days of exposure to study drug and average daily dose (mg/day) will be summarized by study visit in the SS. Average daily dose will be calculated as (number of tablets dispensed minus the number of tablets returned minus the number of tablets lost) divided by number of days from visit i-1 to visit i and multiplied by the mg of the tablets. The proportion of subjects who took 60mg, 120mg will be summarized by study visit in the SS. Subjects who took only 60mg doses from visit i-1 to visit i will be included in the numerator for the 60mg category for visit i; subjects who took only 120mg doses from visit i-1 to visit i will be included in the numerator for the 120mg category for visit i. Descriptive statistics for the total number of tablets dispensed, number of tablets returned and number of tablets lost will be displayed by study visit and overall. Compliance with study drug will be calculated as (number of tablets dispensed minus the number of tablets returned minus the number of tablets lost) divided by the scheduled number of doses, expressed as a percentage. If this percentage is calculated greater than 100%, then compliance will be calculated 1 minus (the calculated percentage minus 1). Compliance will be summarized overall and by scheduled weeks for the safety analysis set.

Study drug dispense and accountability with the reason for not returning tablets is captured on the CRF and will be presented in the data listings.

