12. Unless otherwise specified, percentage values should be printed with one digit to the right of the decimal point (e.g., 12.8%, 5.4%). While count and percentage values are presented together, percentage values should be printed in parentheses 1 space after the count (e.g., 7 (12.8%), 13 (5.4%)). Any counts of 0 will be presented as 0 and not as 0 (0%). Unless otherwise noted, for all percentages, the number of patients in the analysis set for the cohort who have an observation will be the denominator.
13. Missing descriptive statistics due to non-estimability in tables, as well as missing data in patient listings should be represented as either a hyphen (“-“) with a corresponding

footnote (“ - = unknown or not evaluated”), or as “N/A” with the footnote “N/A = not applicable” whichever is appropriate.

14. Dates printed as a result in the TFL should be printed in SAS DATE9. format (“DDMONYYYY”: 01 Jul 2002). Missing portions of dates should be represented on patient listings as dashes (e.g., -- Jul 99). Dates that are missing because they are not applicable for the patient should be listed as “N/A”, unless otherwise specified.
15. All observed time values should be presented using a 24-hour clock HH:MM:SS format (e.g., 01:35:45, or 11:26).
16. Data in columns of a table should be formatted as follows:
 - Alphanumeric values are left-justified;
 - Whole numbers (e.g., counts) are right-justified; and
 - Numbers containing fractional portions are decimal aligned

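### SAP 9.3.1 averages daily dose over off-drug days when treatment stops before a visit, has no rule for an interval with both tablet strengths, and leaves patients who took both doses out of both dose categories

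*SAP*

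**What the plan says.** SAP 9.3.1 sets out the exposure tables: "The number of days of exposure to study drug and average daily dose (mg/day) will be summarized by study visit in the SS". Days of exposure is not defined. Average daily dose is tablets dispensed less those returned and lost, "divided by number of days from visit i-1 to visit i and multiplied by the mg of the tablets".

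The dose table has two categories: "Subjects who took only 60mg doses from visit i-1 to visit i will be included in the numerator for the 60mg category", and "subjects who took only 120mg doses from visit i-1 to visit i will be included in the numerator for the 120mg category". There is no category for a patient who took both. SAP 11.1 gives the default for percentages: "the number of patients in the analysis set for the cohort who have an observation will be the denominator".

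In the protocol:
- Table 1, footnote w, and section 6.2.20 ask for the Early Termination Visit as soon as possible after the last dose. They also cover a late one: "If patient took the last dose of IMP 28 or more days prior to the Early Termination Visit", the Safety Follow-Up Visit is not required.
- Section 5.8 says that at Week 52 or Early Termination "the authorized study staff will enter the date of the last dose of IMP taken in the source documents and eCRF".
- Section 3.1 lets the investigator change the dose at Week 2 or any later visit. Section 6.2.21.2 allows drug to be dispensed at an Unscheduled Visit, in bottles of 60 mg or 120 mg tablets.

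**The concern.** A figure labelled average daily dose should describe the dose while the patient was on drug. Here the numerator stops growing at the last dose, while the denominator runs on to the next visit. For a patient who stopped early, the result mixes dose with time off drug and can only be too low. The date needed to separate the two is collected, but the formula does not use it.

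The single strength multiplier is a second gap. If both strengths were used in one interval, no single value of mg per tablet is right.

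The third gap is the pair of 'only' rules in the dose table. A patient who took both doses falls in neither numerator, and the percentages fall short of 100% with no row to explain it.

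Safety and tolerability is the primary objective, and all output carries one label, Tozadenant (SAP 5.1). Section 9.3.1 is where a reader will look for how much drug patients took, and the average is least reliable for those who stopped early, including those who stopped for adverse events.

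**Working it through.** **Inputs from the documents.** Starting amount: two 120 mg or four 60 mg tablets per day (Protocol 6.2.3.4), which is 240 mg/day. Scheduled intervals: Week 12 to 24 and Week 24 to 36 are 84 days; Week 6 to 12 is 42 days. The formula is that of SAP 9.3.1.

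**Assumptions.** The documents give no stopping or switching times, so the gaps, interval lengths and switch day below are illustrations.

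**1. Patient still on drug.** Baseline to Week 2, first dose on the evening of Day 0 and last counted dose on the morning of Day 14: 28 doses in 14 days. With 60 mg tablets, 56 × 60 / 14 = 240 mg/day. With 120 mg tablets, 28 × 120 / 14 = 240 mg/day. The formula is right for an adherent patient still on drug with one strength.

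**2. Drug stopped before visit i.** Reported value = 240 × (interval − gap) / interval.

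| Gap, last dose to visit | 84-day interval | 42-day interval |
|---|---|---|
| 3 days | 240 × 81/84 = 231 | 240 × 39/42 = 223 |
| 7 days | 240 × 77/84 = 220 | 240 × 35/42 = 200 |
| 28 days | 240 × 56/84 = 160 | 240 × 14/42 = 80 |

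The value while on drug is 240 in every cell. With 28 days on drug and 28 days off, the result is 240 × 28/56 = 120 mg/day, the same as a fully adherent patient on 60 mg BID (2 × 60).

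**3. Consistency with days of exposure.** Take the 84-day interval with a 28-day gap. The patient took 56 × 240 = 13,440 mg. If days of exposure means days on drug, exposure times average dose is 56 × 160 = 8,960 mg. If it means days between visits, 84 × 160 = 13,440 mg. The two summaries agree only under the second meaning, and the SAP does not say which applies.

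**4. Both strengths in one interval.** Switch from 120 to 60 mg BID at day 42 of 84, one tablet per dose: 84 tablets of 120 mg and 84 of 60 mg, 168 in all.
- Using 60 mg: 168 × 60 / 84 = 120 mg/day.
- Using 120 mg: 168 × 120 / 84 = 240 mg/day.
- Summed by strength: (84 × 120 + 84 × 60) / 84 = 180 mg/day.

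If only 60 mg tablets were used, the count is 4 × 42 + 2 × 42 = 252, and 252 × 60 / 84 = 180, which is correct. The error needs mixed strengths.

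**5. Dose table.** If a share m of patients with data took both doses in an interval, the two categories sum to 1 − m. For assumed shares of 2%, 5% and 10% they sum to 98%, 95% and 90%. With all 450 planned patients contributing, that is 9, about 22 and 45 patients in neither row.

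**The case against.** The strongest reply is that the protocol works against long gaps. It asks for the Early Termination Visit as soon as possible and, if possible, while the patient is still taking drug (section 4.3.2). The 28-day clause only waives the Safety Follow-Up Visit. A reader might infer that the protocol expects late visits. It does not; it provides for them. With gaps of 3 to 7 days the figure stays between 200 and 231 in the intervals above. This stands, and it limits the size.

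A reader might also infer that patients who stop for adverse events will be presented as low-dose patients. That holds only for the average mg/day. The dose table classifies by doses taken, so a patient on 120 mg BID who stops early is still counted under 120 mg.

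SAP section 9 moves Early Termination data into a scheduled week only when the visit falls in that week's window, and otherwise refers to an early termination column. Diluted averages should therefore sit mainly in that column. This too stands.

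On the dose table, changes are made at visits, so a new dose normally starts a new interval. Unscheduled Visits generally require drug collection and accountability (Protocol 6.2.21.1). If they count as visit i, the interval ends at the switch and neither mixed-dose problem arises there. The SAP does not say: it summarises exposure by study visit and compliance by scheduled weeks. Patients who took both doses are also not dropped from the table. They stay in the denominator and are missing only from the numerators.

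Finally, averaging over a whole interval is a recognised dose-intensity measure. That does not rescue the text, because the SAP calls it average daily dose and reports it beside an undefined days of exposure.

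**Conclusion.** The point holds as a defect in the stated rules, of modest reach. As written, SAP 9.3.1 understates mg/day whenever drug stopped before visit i. The understatement is about 4% for a 3-day gap in 84 days (231 against 240), and two thirds for a 28-day gap in 42 days (80 against 240). It has no defined answer for an interval with both strengths. It leaves patients who took both doses without a category, mainly through Unscheduled Visits and only if these do not end the interval.

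The sizes rest on full adherence and on assumed gaps and switch times. Their frequency cannot be known from the documents. A reader might infer from the disposition row for program termination (SAP 9.1) that many patients' last intervals are affected. That row gives no count and no gap between last dose and visit, so it does not support this.

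Nor is all exposure reporting shown to be wrong. Days of exposure is undefined rather than incorrect, and tablet accountability is listed in full. The effect is confined to descriptive exposure summaries: there are no formal tests (SAP section 9), and the adverse event tables in SAP 9.8.1 are not split by dose.

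**What to change.** Amend SAP 9.3.1 as follows:
- End the average-dose denominator at the earlier of visit i and the recorded last-dose date. Doses missed before that date still lower the average, as they should.
- Define days of exposure on the same basis, so that days times average dose returns the mg taken.
- Compute mg taken separately for 60 mg and 120 mg tablets, and sum them before dividing.
- Add a category for both doses in the interval, and state the denominator for the dose table.
- State whether an Unscheduled Visit at which drug is collected or dispensed ends an interval.

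The cost is SAP wording and minor programming. The last-dose date is already in the eCRF and tablet strength is known from dispensing, so no new data or visits are needed.

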5.11 Enrollment and Numbering of Patients

During the study, the IXRS will be used for initiating the dispensing of open-label IMP as well as tracking the progression of patients in the open-label phase and ensuring an adequate supply of open-label IMP. The IXRS will also be used to dispense IMP supplies, according to the visit schedule and dose level assigned by the investigator.

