6.2.3.4 Assignment and Dispensing of Investigational Medicinal Product

Note: Sites participating in Expanded PK Sampling should refer to [Appendix 15.9.1](#) for Assignment and Dispensing of IMP instructions.

1. For patients meeting all entry criteria, complete the IMP assignment transaction using the IXRS by following the procedures provided.
 - a. Dispense the open-label IMP bottle(s) assigned by the IXRS to the patient for this study visit. Each bottle consists of either 50 tablets of 120 mg tozadenant or 100 tablets of 60 mg tozadenant.
 - b. Record the date IMP was dispensed in IMP dispensing records including patient number, assigned IMP bottle number(s), and date and time IMP was dispensed.
 - c. Review the dosing instructions for the IMP with the patient, answer any questions, and remind the patient to return the IMP (including all used, unused and partially used bottles) at the next visit.
 - d. Patients will be instructed to take either two (2) 60 mg tablets or one (1) 120 mg tablet of the dispensed IMP by mouth BID, in the morning and in the evening preferably at the same time each day, for a total of either two (2) 120 mg tablets or four (4) 60 mg tablets per day. The evening dose should be approximately 12 hours after the morning dose. Patients will be instructed to take their morning and evening doses 1 hour before or 2 hours after a meal and to refrain from eating for 1 hour after dosing. Patients should take the first dose of IMP at home after the Baseline Visit.
2. Instruct the patient to take the first dose of IMP at home on the evening of dispensation.
3. Ensure that the patient understood the dosing instructions and the use of the extra doses included in the bottle if visit delayed and/or use of visit window.
4. Schedule the Week 2 visit. If needed, use the visit window in relation to the date of the Baseline visit.

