6.2.21.2 Additional Assessments at Investigator's Discretion

The following additional assessments may be performed at an Unscheduled Visit for assessment of an AE, at the investigator's discretion depending on the type of AE (e.g., an out-of-range lab value, presence of suicidality, impulsivity, etc.):

1. For all applicable patients: Verify continuation of (or any change to) contraceptive method since previous visit and document.
2. Obtain samples for the following laboratory tests and record the date and time of collection:
 - a. Hematology and chemistry (inclusive of liver function tests).
 - b. TSH, free T3, and free T4.
 - c. Urine sample for urinalysis.
 - d. For females of childbearing potential: urine pregnancy test.

Note: For processing, labeling and shipping of samples, follow the instructions provided in the Central Laboratory Procedures Manual.
3. Obtain and record BP and pulse measurements after at least 5 minutes supine rest and again after standing for approximately 1 and 3 minutes.
4. Obtain 12-lead ECG. Ensure the ECG is collected when the patient is not experiencing dyskinesia that would interfere with an adequate recording. Assess any changes from Baseline for clinical significance.
5. Obtain weight.
6. Perform physical and neurological examination, and assess any changes from Baseline for clinical significance.
7. Administer C-SSRS if suicide risk concern.
8. Administer mMIDI. (Note: After Baseline, if patient has one or more positive modules on the mMIDI, their continued participation in the study should be discussed with the Medical Monitor.)
9. In consultation with the Medical Monitor, discuss any other appropriate diagnostic tests required to evaluate patient's AE.
10. Dispense the open-label IMP bottle(s) assigned by the IXRS to the patient for this study visit. Each bottle consists of either 100 × 60 mg tablets or 50 × 120 mg tablets.

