9.1.7 Overdose of Investigational Medicinal Product

Excessive dosing (beyond that prescribed in the protocol and including overdose) should be recorded in source documents and in the Drug Accountability module of the eCRF. Any SAE or nonserious AE associated with excessive dosing must be followed as any other SAE or nonserious AE. These events are only considered AEs or SAEs if there are associated clinical signs and symptoms or if the act of taking the excess medicine itself is an AE or SAE (e.g., suicide attempt).

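### As written, the SAP compliance formula divides tablets by doses, so a fully adherent patient on 2 x 60 mg BID would be reported at 0% and one taking half the tablets at 100%

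*SAP*

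**What the plan says.** SAP 9.3.1 takes the number of tablets dispensed, subtracts those returned and lost, and sets the result "divided by the scheduled number of doses, expressed as a percentage". If the result exceeds 100%, "then compliance will be calculated 1 minus (the calculated percentage minus 1"). Compliance is then summarised overall and by scheduled week in the Safety Set.

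The same paragraph derives average daily dose from the same tablet count, "divided by number of days from visit i-1 to visit i and multiplied by the mg of the tablets". That formula accounts for tablet strength; the compliance formula does not.

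Protocol 5.6 offers two ways of taking 120 mg BID: two 60 mg tablets or one 120 mg tablet at each dose. Protocol 6.2.3.4 gives the daily count: "for a total of either two (2) 120 mg tablets or four (4) 60 mg tablets per day". Bottles of either strength may be dispensed at Baseline and at later visits. Protocol 11.6 leaves the details of exposure and compliance to the SAP.

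**The concern.** The numerator is in tablets and the denominator in doses. The two agree only when a dose is one tablet. On 2 x 60 mg they differ by a factor of two, and the rule for values above 100% makes this worse. An unfolded 200% would look implausible and prompt a check, whereas the fold turns it into an ordinary-looking 0%.

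Above half intake the ranking is also reversed, so the more a patient takes, the lower the reported value. Because this is a safety and tolerability study, readers will judge adverse event rates against how much drug was taken, and a compliance table with this fault would mislead them. The figures in the section would also disagree with each other: the same patient would show the full daily dose in mg and 0% compliance.

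**Working it through.** The documents state no compliance figure to reproduce, so the check applies the SAP rule as written.

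**Inputs**
- Doses per day: 2 (BID).
- Tablets per day at 120 mg BID: 4 with 60 mg tablets, 2 with 120 mg tablets (Protocol 6.2.3.4).
- Tablets per day at 60 mg BID: 2 (Protocol 5.6).
- Ratio r = tablets taken / scheduled doses. Reported value = r if r ≤ 1, otherwise 1 − (r − 1) = 2 − r (SAP 9.3.1). There is no floor at zero.

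**One interval on 2 x 60 mg BID.** From Baseline to Week 2 there are 14 days, 28 doses and 56 tablets.
- Full intake: 56/28 = 2.0, reported 2 − 2.0 = 0%.
- Half intake: 28/28 = 1.0, reported 100%.

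For a true intake fraction a, r = 2a whatever the interval length. The reported value is 2a up to a = 0.5 and 2 − 2a above it:

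| True intake | r | Reported |
|---|---|---|
| 110% | 2.2 | −20% |
| 100% | 2.0 | 0% |
| 90% | 1.8 | 20% |
| 80% | 1.6 | 40% |
| 60% | 1.2 | 80% |
| 50% | 1.0 | 100% |
| 40% | 0.8 | 80% |

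Only true intake between 40% and 60% is reported above 80%.

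**Regimens with one tablet per dose** (1 x 120 mg or 1 x 60 mg BID). Here r = a, so 100% reads as 100% and 50% as 50%. These intervals are unaffected.

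**Contradiction with average daily dose.** At full intake on 2 x 60 mg, (56/14) × 60 = 240 mg/day beside 0% compliance. At half intake, (28/14) × 60 = 120 mg/day beside 100%. A fully adherent patient on 60 mg BID gives the same pair: 28 tablets, 120 mg/day, 100%.

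**Overall value over 52 weeks.** Assume a fully adherent patient who stays at 120 mg BID for 364 days (728 doses), with the first d days on 2 x 60 mg and the rest on 1 x 120 mg. Tablets = 4d + 2(364 − d) = 728 + 2d. Pooled, r = 1 + d/364 and the reported value is 1 − d/364. The SAP does not say how the overall value is formed, so the last column shows the alternative of averaging the six between-visit intervals (14, 28, 42, 84, 84 and 112 days), each scoring 0% or 100%:

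| d (days) | Pooled | Mean of six intervals |
|---|---|---|
| 14 | 96.2% | 5/6 = 83.3% |
| 42 | 88.5% | 4/6 = 66.7% |
| 84 | 76.9% | 3/6 = 50% |
| 168 | 53.8% | 2/6 = 33.3% |
| 364 | 0% | 0% |

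Under pooling the value falls below 80% once d/364 > 0.20, that is d > 72.8, or from 73 days.

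**Check of an mg-based ratio**
- 28 days of 2 x 60 mg BID, full intake: (112 × 60)/(56 × 120) = 100%.
- 14 days of 2 x 60 mg BID then 14 days of 1 x 60 mg BID, full intake: (56 × 60 + 28 × 60)/(28 × 120 + 28 × 60) = 5040/5040 = 100%. The SAP rule gives 84/56 = 1.5, reported as 50%.

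**The case against.** The arithmetic is not in dispute. The strongest reply is that nobody would program it this way. SAP section 1 asks that the plan be read with the protocol, and Protocol 5.8 expresses compliance against the assigned dose, so a sensible programmer would scale by tablets per dose and the error would vanish. That may happen, but the SAP does not say so, and it uses the word dose elsewhere in 9.3.1 for the 60 mg and 120 mg levels, not for tablets. SAP section 10 requires independent programming of every unique table. Two programmers following the text would reproduce the fault, and two reading it differently would disagree.

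The second reply concerns size, and much of it stands. The overall figures depend on pooling, on 364 days of exposure, and on a switch date that need not be a scheduled visit. SAP 9.1 tabulates patients who stopped because of program termination, so full-length exposure may not be typical. Averaging over intervals gives larger errors, so pooling does not overstate the problem, but the per-interval result is the firm one. The 80% limit in Protocol 5.8 ("If a patient is found to be persistently noncompliant") guides an in-study decision made from tablet accountability with the patient present. It does not use the SAP figure, so a low value in the table triggers nothing.

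Third, compliance feeds no endpoint, analysis set or test. Tablet counts, mg/day and the accountability listings are reported separately, and excessive dosing "should be recorded in source documents and in the Drug Accountability module of the eCRF". This is right, and it limits the harm to the description of adherence.

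**Conclusion.** The point holds: the rule is wrong as written for every interval in which 120 mg BID is taken as 2 x 60 mg. There, full intake is reported as 0% and half intake as 100%, whatever the interval length. Intervals on one tablet per dose are correct, and mixed intervals are distorted in part. This rests only on the SAP wording being programmed literally.

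The effect on the study-level summary cannot be sized, because neither document gives the share of patients or of treatment time on 2 x 60 mg. It should be corrected before the tables are produced, but it does not threaten the primary safety results.

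**What to change.** Replace the compliance sentence in SAP 9.3.1 with:

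> Compliance (%) = 100 × [sum of (tablets taken × tablet strength in mg)] / [sum of assigned mg for the scheduled doses], summed over segments whenever tablet strength or assigned dose changes within an interval.

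The segment rule is needed because the dose can change during the study and because Protocol 6.2.21.2 allows dispensing at an unscheduled visit ("Dispense the open-label IMP bottle(s) assigned by the IXRS to the patient for this study visit"). The SAP should also state whether the overall value pools all segments; pooling mg is the natural choice.

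A smaller edit, replacing scheduled doses with scheduled tablets, also restores 100% and 50% on 2 x 60 mg. It weights mixed strengths unevenly, however. A patient who takes everything during 14 days of 2 x 60 mg BID and nothing during the next 14 days of 1 x 120 mg BID scores 56/(56 + 28) = 66.7% by tablets, but (56 × 60)/(56 × 60 + 28 × 120) = 50% by mg.

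Optionally, drop the fold, report values above 100% as they are, and tabulate ≤80%, >80 to <120% and ≥120%, using the limits in Protocol 5.8. The fold agrees with those limits (120% reads as 80%) but hides whether a patient took too much or too little. The main correction does not depend on this.

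The cost is one SAP sentence and one derivation. Tablet strength comes from the dispensed bottle and the assigned dose from the IXRS, which under Protocol 5.11 dispenses "according to the visit schedule and dose level assigned by the investigator". Dispensing and IXRS records may have to be linked, but no new data need to be collected.

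### SAP 9.3.1 reflects compliance above 100% to below 100%, so the compliance tables cannot tell over-use from under-use

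*SAP*

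**What the plan says.** SAP 9.3.1 takes tablets dispensed, less those returned and those lost, "divided by the scheduled number of doses, expressed as a percentage". It then adds: "If this percentage is calculated greater than 100%, then compliance will be calculated 1 minus (the calculated percentage minus 1", with the bracket closing after that.

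On output it says: "Compliance will be summarized overall and by scheduled weeks for the safety analysis set". It does not plan an unreflected percentage, a count of patients above 100%, or a category at or above 120%.

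The same section plans three outputs that the reflection does not touch:

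- Average daily dose: "The number of days of exposure to study drug and average daily dose (mg/day) will be summarized by study visit in the SS".
- Tablets dispensed, returned and lost, described by visit and overall.
- A patient-level listing: "Study drug dispense and accountability with the reason for not returning tablets is captured on the CRF and will be presented in the data listings".

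Protocol 5.8 opens its rule with "If a patient is found to be persistently noncompliant" and gives two limits in the bracket that follows, ≤80 and ≥120% of the assigned dose. Protocol 11.6 leaves the detail of the exposure and compliance summaries to the SAP, so nothing in the protocol overrides the rule.

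**The concern.** A compliance percentage normally tells the reader whether patients took less or more than was assigned. Once values above 100% are folded back, a reported 80% may mean either a fifth too little or a fifth too much, and the table does not say which.

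The study's primary objective is safety and tolerability, so the direction of a departure from the assigned dose matters for interpretation. Excess intake bears on how adverse events are read, and a shortfall bears on whether event rates are diluted. Protocol 9.1.7 asks for excessive dosing to be recorded in the Drug Accountability module of the eCRF, yet the compliance summary would present that excess as a shortfall. For the same patient and interval, the average daily dose would lie above the assigned dose while compliance lay below 100%.

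**Working it through.** The documents state no compliance figure to reproduce, so the check is arithmetic on the SAP rule.

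**Inputs**
- Calculated compliance: c = (dispensed − returned − lost) / scheduled doses (SAP 9.3.1).
- Reported compliance: c if c ≤ 1, and 1 − (c − 1) = 2 − c if c > 1 (SAP 9.3.1).
- Limits: ≤80% and ≥120% of the assigned dose (Protocol 5.8).
- At 120 mg BID, a dose is one 120 mg tablet or two 60 mg tablets (Protocol 5.6). The examples use 120 mg tablets at that dose level, and 60 mg tablets at 60 mg BID, so that one tablet is one dose and the result owes nothing to the units of the ratio.

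**Step 1: single values**

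| Calculated | 2 − c | Reported |
|---|---|---|
| 105% | 2 − 1.05 | 95% |
| 110% | 2 − 1.10 | 90% |
| 120% | 2 − 1.20 | 80% |
| 130% | 2 − 1.30 | 70% |
| 150% | 2 − 1.50 | 50% |

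The upper limit of Protocol 5.8 falls exactly on the lower limit.

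**Step 2: two patients** (assumed 15-day interval, 120 mg BID, 30 scheduled doses)
- Patient A uses 36 tablets: c = 36/30 = 120%, reported as 80%. Average daily dose = 36 × 120/15 = 288 mg/day.
- Patient B uses 24 tablets: c = 24/30 = 80%, reported as 80%. Average daily dose = 24 × 120/15 = 192 mg/day.
- Scheduled: 30 × 120/15 = 240 mg/day.

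The compliance results are identical, but the doses differ by 96 mg/day.

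**Step 3: group summaries**

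Because 2 − c = c − 2(c − 1), the reported mean equals the unreflected mean minus twice the mean excess over 100% (counted as zero for patients at or below 100%).
- Half at 90%, half at 110%: unreflected mean = (0.90 + 1.10)/2 = 100%. Mean excess = 0.10/2 = 0.05. Reported mean = 1.00 − 2 × 0.05 = 90%.
- Half at 80%, half at 120%: unreflected mean 100%, SD 20 points, range 80% to 120%. Reported mean 80%, SD 0, maximum 80%.

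These mixes are illustrations. The documents give no expected distribution of compliance.

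**Step 4: can average daily dose stand in?**

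Only in part. SAP 5.1 uses one treatment label, so patients on 60 mg BID and 120 mg BID are summarized together. A patient on 60 mg BID who uses 36 tablets over the same 15 days is at 120% of assigned, but has 36 × 60/15 = 144 mg/day. That is above the 120 mg/day assigned to this patient and well below the 240 mg/day scheduled at 120 mg BID. In a pooled table this over-use does not stand out. The tablet counts likewise mix 60 mg and 120 mg tablets.

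**The case against.** The best defence is that the rule is a deliberate score of closeness to the assigned dose. Protocol 5.8 has one category of persistent noncompliance with one consequence, and 2 − c ≤ 0.80 exactly when c ≥ 1.20. A reported value at or below 80% therefore picks out everyone outside the 5.8 limits. On that reading, 90% is a fair summary of a group in which everyone is 10 points off, and an unreflected mean of 100% would flatter it. The algebra stands, and so does the warning that a raw mean can hide opposite departures. But the SAP does not describe such a score. It presents the value as compliance with study drug. Even as a closeness score it loses direction, which the category counts proposed below would keep.

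The second defence is that over-use is recorded elsewhere: in average daily dose, tablet counts, the accountability listing, the recording required by Protocol 9.1.7, and the reconciliation with the patient under Protocol 5.8. This also stands, within the limits in step 4.

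Three stronger readings are tempting, and the documents support none of them:

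- A reader might infer that over-use becomes invisible throughout the report, or that exposure reporting as a whole is corrupted. The other outputs of SAP 9.3.1 are unreflected, so this does not follow.
- A reader might infer that safety conclusions are affected. Compliance defines no analysis set (SAP 3.1), no formal tests are planned (SAP 9), and the primary safety variables are TEAEs (Protocol 11.5).
- A reader might take an unreturned bottle as the measure of harm. Fifty 120 mg tablets against 28 doses in 14 days gives 50/28 = 179%, reported as 21%. This assumes that the bottle is neither returned nor recorded as lost, and the unreflected 179% would mislead too. A negative value needs c above 200%, for example two such bottles in that interval: 100/28 = 357%, reported as −157%. No document gives that dispensing quantity. Neither figure measures the effect of the rule.

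**Conclusion.** The point holds as a defect of the compliance tables. Followed as written, SAP 9.3.1 reports 110% as 90% and 120% as 80%, and no planned compliance summary separates the two directions that Protocol 5.8 names. The shift in the group mean is twice the mean excess over 100%: 10 points in the 90%/110% illustration and 20 points in the 80%/120% one. The actual size depends on how many patients exceed 100% and by how much, which the documents do not predict. If nobody exceeds 100%, the rule does nothing.

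The mapping itself rests only on the SAP text. Calling the lower mean misleading assumes that readers take compliance to mean the share of the assigned dose used, which is how the SAP's own formula defines it before the reflection. The matter should be corrected before the tables are programmed, but it does not put the safety analyses in doubt.

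**What to change.** In SAP 9.3.1:

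1. Delete the reflection sentence and report compliance as calculated.
2. Beside the descriptive statistics, give n (%) at ≤80%, >80% to <120%, and ≥120%, by scheduled week and overall. These are the Protocol 5.8 limits used only as reporting cut-points. No dosing or discontinuation rule changes.
3. Keep intervals with unreturned tablets in the summary and its denominators, and footnote them, because a high percentage there may reflect missing returns and not over-use. Dropping them would need a denominator rule that the SAP does not have.

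The cost is one sentence deleted, three table rows and a footnote. All the data are already collected.

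A separate matter should be settled at the same time. The ratio divides tablets by doses, so a fully compliant patient taking two 60 mg tablets BID over 15 days calculates to 60/30 = 200% if the text is read literally. The denominator should be scheduled tablets or milligrams. Otherwise such patients would fall in the ≥120% row. Correcting the units does not remove the reflection problem, which arises equally when one tablet is one dose.
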